1 PROTOCOL SUMMARY

1.1 Synopsis

Protocol Title: A Two-part Phase IIa Randomised, Double-blind, Placebo-controlled, Dose-ranging, Multi-centre Study to Assess Efficacy and Safety of Inhaled AZD1402 Administered as a Dry Powder Twice Daily for Four Weeks in Adults with Asthma on Medium-to-High Dose Inhaled Corticosteroids

Short Title: Efficacy and Safety of Inhaled AZD1402 administered Twice Daily for Four Weeks in Adults with Asthma on Medium-to-High Dose Inhaled Corticosteroids

Rationale:

Asthma is a chronic, complex, and heterogeneous respiratory disease characterised by a range of pathogenic features including pulmonary inflammation, mucus hypersecretion, variable airway obstruction, and airway remodelling. Symptoms and airway obstruction can resolve in response to therapy or spontaneously, but participants remain at risk of severe worsening of their asthma (exacerbations). These asthma exacerbations can be life-threatening, can significantly impact the participant's quality of life, and result in significant healthcare costs.

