- v Sampling on Days 2, 6, 8, 10, and 12.
- w CRP must be done locally on Day -1 (may be performed on Day -2 for logistical reasons) to confirm eligibility as per inclusion criterion 26. It may be performed throughout the study in the event of AE/AESI as required to inform suspension/stopping criteria.
- x Blood samples will be analysed for IgE if potential drug related IgE response is observed in any participant; may be collected on Day -1 or Day 1 pre-dose.
- y PCR may be performed to confirm hepatitis B / hepatitis C status if required.
- z Blood samples for PK measurements will be collected for all participants. Timing of samples: Day 1 pre-dose (-60 min), 1, 2, 3 (\pm 10 min), 4, 6, 8 (\pm 20 min) and 12 h (up to 1h prior to the next dose, must be before the subsequent dose); Day 28 pre-dose (-60 min), 1, 2, 3 (\pm 10 min), 4, 6, 8 (\pm 20 min), and 12h (\pm 1 h; single dose of AZD1402 only on Day 28). Pre-dose on Days 2, 4, 6, 8, 10, 12, 14, 16, 20, 24 (up to 1 h prior to the next dose, must be before the subsequent dose), 29 (24 h \pm 2 h after Day 28 dose), 30 (48 h \pm 2.5 h after Day 28 dose), 32 (96 h \pm 2.5 h after Day 28 dose), 39 (\pm 6 days), and 56 (\pm 4 days). Part Ib only: Day 20, 4 h post-morning dose (\pm 20 min). The PK sampling timepoints may be amended based on results from Part 1a/b. An unscheduled PK sample may be collected in the case of AEs and / or unscheduled safety blood sampling.
- aa ADA sampling, pre-dose Day 1, Day 14, Day 20, Day 24 (Part 1b only) and Day 28 and on Follow-up/unscheduled visits. CCI [REDACTED]
[REDACTED] An unscheduled ADA sample may also be collected in case of AEs/AESIs and/or unscheduled safety blood sampling.
- bb Sample collection if consented only. If for any reason the sample is not drawn at Visit 3, it may be taken at any visit until the last study visit.
- cc All urine pregnancy tests will be done pre-dose.

dd SARS-CoV-2 serology at Screening, End of Trial and final Follow-up Visits; PCR is optional and may be performed centrally or at the local laboratory as clinically indicated and as per local guidelines for the duration of the study. Ad hoc nasal and/or throat-swab specimen is to be collected for the identification of a suspected respiratory infection during any visit. This may be performed locally, or if required by central laboratory.

ee May be performed on Day -2 for logistical reasons.

Table 2 Schedule of Activities Part 2

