x Blood samples for PK measurements will be collected in all participants pre-dose at each visit, including unscheduled visits. Intense sampling may be performed in approximately 25% of participants per treatment arm (for example, 20 subjects in the **Q**mg treatment arm). Timing of intense samples: Day 1: 1, 2, 3 (\pm 10 min), 6, and 8 h (\pm 20 min), Day 21 4 h post-morning dose (\pm 20 min) and Day 28 (last dose), 1, 2, 3 (\pm 10 min), 6, 8 (\pm 20 min), 24 (\pm 2 h), 48 (\pm 2.5 h), and 96 h (\pm 2.5 h; single dose of AZD1402 only on last day of dosing). PK sampling timepoints may be amended based on results from Part 1a/b. An unscheduled PK sample may be collected in the case of AEs and / or unscheduled safety blood sampling.

y ADA sampling, pre-dose Day 1, Day 14, Day 21, Day 28, and at the Follow-up Visits. An unscheduled ADA sample may also be collected in the case of AEs/AESIs and/or unscheduled safety blood sampling.

z Sample collection only if consented. If for any reason the sample is not drawn at Visit 3, it may be taken at any visit until the last study visit.

aa Proposed samples and times: Serum: Pre-dose Day 1, pre-dose Week 2, Week 4 and at Follow-up. **CCI** Pre-dose Day 1, and Week 4. **CCI** Pre-dose Day 1, Day 28, and Day 39. **CCI** Pre-dose Day 1.

bb All urine pregnancy tests will be done pre-dose. In case of a positive result, a serum pregnancy test will be performed.

cc SARS-CoV-2 serology at Screening; PCR is optional and may be performed centrally or at the local laboratory as clinically indicated and as per local guidelines for the duration of the study. Ad hoc nasal and/or throat-swab specimen is to be collected for the identification of a suspected respiratory infection during any visit. This may be performed locally, or if required by central laboratory.

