4.4.1 Premature Termination of the Study and Stopping Criteria

The Sponsor will suspend or terminate a dose level or the entire study (as applicable) following the review of all available safety data if any of the following occurs at the dose or study level:

Per dose level (Part 1)

- Two participants experience a FEV₁ drop $\geq 30\%$ from baseline (in-clinic)* attributable to AZD1402.
- One participant experiences a hypersensitivity-like SAE attributable to AZD1402.

- Day 28 exposure in one participant in Part 1 exceeds or is predicted to exceed (for Part 1b) a peak concentration Cmax of 5420 ng/mL or exposure AUC(0-24 h) of 68700 ng.h/mL.

*Baseline Part 1: Mean of Day -1 and Day 1.

Per dose level (Part 2)

- Clinically significant FEV₁ decline from baseline* attributable to AZD1402 comparing the number of participants reaching a FEV₁ drop $\geq 30\%$ in active versus placebo as assessed by the DSMB.
- One participant experiences a hypersensitivity-like SAE attributable to AZD1402.

*Baseline Part 2: Mean of Day 1 (15 minutes and 45 minutes pre-dose).

Study level

- Two participants experience a hypersensitivity-like SAE and/or severe hypersensitivity event attributable to AZD1402.
- The overall safety and tolerability profile as determined by the DSMB does not justify continuation with dosing as per the current protocol.
- Significant immunogenicity impacting safety and tolerability.
- The Sponsor considers the applied doses of the study intervention to be no longer relevant.
- The Sponsor decides to discontinue the study.
- Data not known before, become available and raise concern about the safety of AZD1402 so that continuation would pose potential risks to the participants.

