4.9.2 Treatment Compliance

Compliance will be assessed by checking the daily e-Diary and eCRF.

For all treatments, treatment compliance will be calculated as:

$$\text{Treatment compliance (\%)} = \frac{\text{Number of doses taken during treatment period}}{\text{Number of doses planned (28 days*) during treatment period}} \times 100.$$

*The number of doses planned is 55 since there is only 1 dose in the morning of Day 28.

Compliance is expected to be $\geq 80\%$ during the Treatment Period.

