- AUCs (including AUClast and AUC τ) will be calculated using the linear trapezoidal method when concentrations are increasing and the logarithmic trapezoidal method when concentrations are decreasing (linear up log down). The minimum requirement for the

Statistical Analysis Plan

calculation of AUC will be the inclusion of at least 3 consecutive serum concentrations above the LLOQ.

- If the concentration at the time of dosing is missing, then this will be set to 0.
- Data exclusions from analysis should be avoided. However, in clear cases of technical issues, such as documented sample mix up, bioanalytical error or mis-dosing, individual or subject level data may be excluded from summaries or summarised separately. Data exclusions will be agreed with the AstraZeneca Clinical Pharmacology Scientist and discussed in the CSR.
- Pharmacokinetic parameters associated with positive pre-dose value(s) of greater than 5% Cmax for the first dose may be excluded from the summary statistics of PK tables and statistical analysis at the discretion of the pharmacokineticist.

Pharmacokinetic parameters will be listed by subject and summarised by AZD1402 dose and study Part. Descriptive statistics for calculated PK parameters will include: n, mean, SD, geometric mean, GeoCV%, median, minimum and maximum values. For tmax, only median, minimum, and maximum values will be presented. No descriptive statistics will be determined when fewer than 3 individual PK parameters are available.

The following rules will be followed with regards to the number of decimal places and presentation of data in the tables and listings for PK parameters:

- Individual PK parameters will be presented to 4 significant digits, with the exception of tmax, which will be presented to 2 decimal places.
- Parameters derived directly from source data (eg, Cmax₀) shall be reported with the same precision as the source data (if this is not 4 significant digits).
- The mean, geometric mean, median, and SD values will be reported to 4 significant digits, all other descriptive statistics will be reported to 3 significant digits.
- For tmax, the minimum and maximum will be presented to 2 decimal places and all other descriptive statistics will be presented to 3 decimal places.
- Estimates and CIs in the form of percentages will be presented to 2 decimal places.

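### The rule that sets a missing pre-dose concentration to zero is not limited to the first dose, so on Day 28 it slightly understates AUCτ, AUClast and the AUC accumulation ratio

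*SAP*

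**What the plan says.** SAP 4.15.3 lists the conventions for deriving PK parameters. Directly after the AUC method comes this rule: "If the concentration at the time of dosing is missing, then this will be set to 0". It names no day or dose. Two bullets later, another rule does carry a limit: "Pharmacokinetic parameters associated with positive pre-dose value(s) of greater than 5% Cmax for the first dose may be excluded". AUC uses the "linear trapezoidal method when concentrations are increasing and the logarithmic trapezoidal method when concentrations are decreasing".

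The protocol title gives the regimen as "Administered as a Dry Powder Twice Daily for Four Weeks", and SAP 4.9.2 adds: "The number of doses planned is 55 since there is only 1 dose in the morning of Day 28". In the protocol's Schedule of Activities, the Part 1 footnote starts the last profile at "Day 28 pre-dose (-60 min), 1, 2, 3" h and runs through 4, 6, 8 and 12 h. The Part 2 footnote for the intensively sampled subset reads "Day 28 (last dose), 1, 2, 3" h, then 6, 8, 24, 48 and 96 h, with pre-dose samples at each visit.

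SAP 3.2.3 lists AUCτ, AUClast, Ctrough, Rac AUC and Rac Cmax. Protocol 4.4.1 has a Part 1 stopping criterion that applies when "Day 28 exposure in one participant in Part 1 exceeds or is predicted to exceed" a Cmax of 5420 ng/mL or an AUC(0-24 h) of 68700 ng.h/mL.

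**The concern.** Before the first dose, zero is the natural value for a missing sample, because exclusion criterion 29 keeps out anyone who has already received the drug. Before the Day 28 dose it is not. The participant has been dosed for four weeks, and the pre-dose level is what the plan itself reports as Ctrough. A programmer who follows the sentence as written would put a zero at the start of any Day 28 profile whose pre-dose sample is missing.

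The error cannot be upward. It lowers Day 28 AUCτ and AUClast and their dose-normalised forms. It also lowers Rac AUC, because the Day 1 denominator is unaffected while the Day 28 numerator shrinks. At stake is the accuracy of reported exposure and accumulation in small groups: about 10 participants per active dose in Part 1, and about a quarter of each arm in Part 2.

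**Working it through.** **Inputs from the documents**
- Doses before the Day 28 sample: 27 × 2 = 54. Adding the Day 28 dose gives 55, which reproduces the SAP's planned count.
- Dosing interval: taken as 12 h from twice-daily dosing.
- First post-dose sample: 1 h in both parts.
- A rising segment is a linear trapezoid.

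**Inputs assumed**
- Half-life 1.5 to 24 h and absorption rate (ka) 0.3 to 1.0 per h, in a one-compartment model evaluated at dose 55. The documents give no figures; the protocol's amendment history calls the half-life only short.

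**Loss per affected profile**
- Correct first segment, if concentration rises over the first hour: (Ctrough + C1)/2 × 1 h.
- With zero imputed: C1/2 × 1 h.
- Difference: 0.5 × Ctrough (in ng.h/mL), lost from both AUCτ and AUClast.

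**As a share of AUCτ**
- AUCτ = 12 × Cavg, so the share is (0.5/12) × (Ctrough/Cavg).
- Bound when Ctrough ≤ Cavg: 0.5/12 = 4.2%.

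Model results with Part 1 sampling times and the SAP's linear-up, log-down rule:

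| Half-life (h) | ka (per h) | Ctrough/Cavg | Loss in AUCτ | Rac AUC, true → with zero |
|---|---|---|---|---|
| 1.5 | 1.0 | 0.04 | 0.18% | 1.01 → 1.01 |
| 1.5 | 0.3 | 0.25 | 1.05% | 1.08 → 1.07 |
| 3 | 1.0 | 0.25 | 1.02% | 1.09 → 1.08 |
| 6 | 1.0 | 0.53 | 2.20% | 1.40 → 1.37 |
| 12 | 0.3 | 0.84 | 3.49% | 2.60 → 2.51 |
| 24 | 0.3 | 0.92 | 3.82% | 4.57 → 4.39 |

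Hand check at 6 h, ka 1.0: 0.53 × 0.5/12 = 2.2%, and 1.40 × (1 − 0.022) = 1.37.

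**What does not move.** SAP 4.15.3 takes Cmax as the highest post-dose concentration. The imputed value therefore cannot enter Cmax, Rac Cmax or the Cmax stopping limit.

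**Which replacement value works**
- Part 1: at steady state the 12 h concentration after the last dose equals the trough, and using it restores AUCτ in full.
- Part 2 has no 12 h sample. The lowest value within the interval is then usually the 8 h sample. At half-life 3 h, ka 1.0, C8 is about 2.5 × Ctrough, so AUCτ is overstated by (2.5 − 1) × 0.5 = 0.75 × Ctrough, more than the 0.5 × Ctrough being corrected. Across the assumed range the 8 h value overstates AUCτ by 0.4% to 1.9%.
- Log-linear interpolation between 8 h and 24 h gives ln C12 = 0.75 ln C8 + 0.25 ln C24. In the least favourable case tried (half-life 3 h, ka 0.3, Ctrough/Cavg 0.47) this gives 0.89 × Ctrough, an error of 0.11 × 0.5 × 0.47/12 = 0.2% of AUCτ.

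**The case against.** The strongest reply is that the effect is small and should be rare. Day 28 in Part 1 is an in-clinic admission, so a missing pre-dose sample should be uncommon, and PK is a secondary objective summarised descriptively. With a short half-life the loss is near the bottom of the range. SAP 4.15.3 also sets a pre-dose value below the quantification limit to zero without a Day 1 limit, so where the Day 28 trough is unquantifiable, zero is the plan's own value. The protocol refers PK calculation to company standards that are not reproduced and may handle steady-state profiles properly. All of this limits the size. None of it supplies the missing restriction, and the written rule is what a reader or programmer has.

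Two stronger inferences are tempting, and the documents support neither.

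- **That the zero weakens the exposure stopping limit.** The Cmax part is unaffected. AUC(0-24 h) is not among the parameters listed in either document, nothing says it is calculated under SAP 4.15.3, and the safety reviews follow a charter that is not included. If it were calculated that way, a true value at the limit with Ctrough = Cavg (68700/24 = 2862.5 ng/mL) would lose 1431 ng.h/mL (2.1%), or 2863 (4.2%) if AUCτ were simply doubled. A safety review outcome for Part 1 also already informed the August 2022 protocol amendment, before this SAP version.
- **That Ctrough itself becomes zero and its geometric mean fails.** SAP 3.2.3 defines Ctrough as an observed concentration, SAP 4.15.2 drops missing samples from concentration summaries, and the zero rule sits beside the AUC method. That outcome would need a misapplication, although one explicit line would exclude it.

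**Conclusion.** The rule is too broad as written and gives a wrong value on Day 28 whenever the trough is quantifiable and the pre-dose sample is missing. AUCτ and AUClast are then understated by 0.5 × Ctrough, and Rac AUC falls in the same proportion as AUCτ. That is about 0.2% to 3.8% of AUCτ over the assumed half-lives and absorption rates, and at most about 4.2% if the trough does not exceed the average concentration. These figures rest on a 12 h interval, a 1 h sample that is present and above the trough, and one-compartment kinetics; how many profiles are affected is unknown. Rac Cmax and both uses of Cmax stand. Whether the Part 1 AUC(0-24 h) limit is affected stays open. This is a minor correction to the reported PK, worth making because the error runs in one direction and is easily avoided.

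**What to change.** In SAP 4.15.3, restrict the zero rule to the pre-dose sample on Day 1, and add the handling for Day 28:

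- **Part 1:** use the same participant's 12 h concentration as the time-zero value for AUC.
- **Part 2:** use the 12 h concentration interpolated log-linearly between the 8 h and 24 h samples. If the 24 h sample is missing or below the quantification limit, use the participant's most recent earlier pre-dose sample. Do not use the 8 h value.
- **Both parts:** leave Ctrough missing, and flag the affected profiles in the listing.

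Also state in one line how the AUC(0-24 h) used for the Part 1 limit is derived, so that a reader can tell whether any imputation enters it.

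The cost is a few sentences in the SAP and the matching line in the PK programming specification. No additional sampling is needed, and no efficacy analysis changes.

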4.16 Immunogenicity Evaluation

Anti-drug antibodies will be summarised as categorical variables with the number and percentages with a positive result at the specific visit. Immunogenicity titre will be summarised descriptively as a continuous variable, only for ADA positive tests, with median, interquartile range, minimum, and maximum, at each analysis visit.

ADA will also be summarised based on the IS including the following:

- ADA positive at baseline and/or post-baseline (ADA prevalence).
- Treatment emergent (TE)-ADA positive (ADA incidence): defined as the sum of treatment-induced ADA positive and treatment-boosted ADA positive.
- Treatment-induced ADA positive: defined as ADA negative at baseline and post-baseline ADA positive.
- Treatment-boosted ADA positive: defined as ADA positive at baseline and boosted the pre-existing titre post-baseline (≥ 4 -fold increase).

- TE-ADA negative: defined as ADA positive but not fulfilling the definition of TE-ADA positive.
- Both baseline and post-baseline positive.
- Only baseline positive.
- ADA persistently positive: defined as either ADA negative at baseline and ADA positive at ≥ 2 post-baseline assessments, or ADA positive at last post-baseline assessment.
- ADA transiently positive: defined as ADA negative at baseline, having at least one post-baseline ADA positive assessment and not fulfilling the conditions of ADA persistently positive.
- TE-ADA positive with maximum titre $>$ median of maximum titres.

Post-baseline includes on-treatment and follow-up phases.

The median of maximum titres is calculated based on the maximum titre for each ADA positive subject within each treatment group (including both baseline and post-baseline measurements).

All immunogenicity parameters will also be reported in listing. Days from previous dose of IP will be calculated as the ADA date minus date of previous dose. Days from previous dose of IP for ADA measured during pre-treatment period will be set to missing. Listings of all subjects excluded from the ADA analysis set will also be provided. Listing will be based on SS.

4.17 Safety Evaluation

All safety summaries and analyses will be based upon the SS as defined in Section 4.5.1 and will be presented by dose level of AZD1402, pooled AZD1402, and placebo and by study part.

In general, there will be no imputation of missing data for the safety analyses. All safety data (scheduled and unscheduled) will be presented in the data listings.

Baseline for safety evaluations will be the last value obtained before first study intervention.

4.17.1 Adverse Events/Serious Adverse Events

Adverse events will be coded using MedDRA latest available version.

All reported AEs will be listed along with the date of onset, date of resolution (if AE is resolved), investigator's assessment of intensity, outcome, action taken with IP, and possible relationship to study drug (assessed by investigator). A by subject listing of all AE (including AEs before first dose of study medication) will be provided. This listing will include the following information: study period, verbatim term, MedDRA SOC, and preferred term, start date/time, end date/time, time from last dose, intensity, causality, action taken, whether the AE was classified as serious, the outcome of the AE and the concomitant or additional treatment given, if any. Any AE occurring before the first dose of IP and/or the AE assessments that are unresolved at the participant's last assessment in the study will be included in the data listings but will not be included in the summary tables of AEs.

Multiple occurrences of an AE in the same subject will only be counted once overall considering start date as the first day of first occurrence and stop date the last day of the last occurrence and the AE will assigned to the treatment of the first occurrence period study drug. Multiple occurrences of an AE in the same subject for the same treatment will only be counted once for that treatment.

Statistical Analysis Plan

The number of subjects will be tabulated also by SOC, preferred term, and treatment.

In the case that, during the study, a subject has more than 1 episode of the same preferred term with different levels of intensity, action taken, outcome causality or seriousness, then the maximum intensity level, action taken (ie, withdrawn) and outcome (ie, fatal), causality level (ie, related), or seriousness level (ie, serious), respectively will be used.

The following ordering will be used to define maximum intensity level, action taken, outcome causality level, or seriousness level:

- Intensity: Mild < Moderate < Severe
- Causality: No < Yes
- Seriousness: No < Yes
- Action taken: Unknown < Not applicable < Dose not changed < Drug interrupted < Drug withdrawn
- Outcome: Unknown < Recovered/resolved < Recovered/resolved with sequelae < Recovering/ resolving < Not recovered/not resolved < Fatal

A general summary of all AEs will show the number and percentage of subjects with:

- Any AE
- Any SAE
- Any SAE with outcome death
- Any AE leading to discontinuation of IP
- Any AE leading to withdrawal from study

An overview summary of AEs together with a presentation of AEs (event count) by preferred terms and sorted by decreasing frequency on preferred term will be also produced. In addition, an overview summary of the number and percentage of subjects with AEs and by SOC, preferred term, and treatment will be also presented by ADA status.

Additional tables will present the number and percentage of subjects with any AESI occurring after first dose (including infection, eosinophilia, and hypersensitivity events) and the in-clinic alerts with the individual occurrences in those categories.

The AESI presented in the table will be (for in-clinic assessments):

- FEV₁ drop $\geq 20\%$ reduction from baseline as informed by in-clinic assessment: information extracted from the AE page on the eCRF.
- FEV₁ drop $\geq 30\%$ reduction from baseline as informed by:
 - in-clinic assessment.
 - decline is sustained over 2 scheduled consecutive home assessments resulting in either dosing suspension or discontinuation (Part 2).
- Confirmed fever ($> 38^{\circ}\text{C}$ for > 4 hours)
- Wheeze*
- Cough*
- Dyspnoea/shortness of breath*

Statistical Analysis Plan

- Infection
 - respiratory tract infection, ideally supported by pathogen identification and confirmation.
 - COVID-19 infection.
 - non-respiratory tract infection.

*Part 1: All new events of wheeze, cough, dyspnoea/shortness of breath.

Part 2: All new worsening events of wheeze, cough, dyspnoea/shortness of breath compared to baseline / individual pre-existing disease characteristics as judged by the Investigator.

In the event of suspected respiratory infection, pathogen identification include:

- SARS-CoV-2 PCR.
- Viral panel which may include but are not limited to influenza (all types), parainfluenza, respiratory syncytial virus, human metapneumovirus, adenovirus, and *Bordetella pertussis*.
- *Mycoplasma pneumonia* and *Chlamydophila pneumoniae* (sometimes included in viral panel).
- Bacterial swab to detect any growth which may include, but are not limited to *Streptococcus*, *Klebsiella*, *Pneumoniae*, *Pseudomonas*, *Staphylococcus aureus*, *E. Escherichia coli*, *Citrobacter*, *Acinetobacter* and *Haemophilus influenza*.

The number and percentage of subjects who experience one or more AEs will be tabulated by each study part, treatment group (dose level of AZD1402, pooled AZD1402, and placebo) and by:

- SOC and preferred term.
- SOC, preferred term, and maximum intensity.
- SOC, preferred term, and relationship to study intervention judged by investigator.

Adverse event summaries will be ordered in terms of decreasing frequency for SOC, and preferred term within SOC.

The tables of AE will include all the AEs with an onset date and time on or after the date and time of first dose of IP up to the end of treatment + 96 hours. Additional tables including all the AEs experienced after the IP until last follow-up (Day 56) and for ADA status will be reported for both Part 1 and Part 2.

Adverse events sorted by decreasing frequency and AEs leading to discontinuation of investigational product by SOC and preferred term will be summarised.

The number and percentage of subjects who experience 1 or more SAEs will be tabulated by treatment group (AZD1402 and placebo) and by SOC and preferred term and by SOC and preferred term and with outcome of death.

For each subject and each AE, the worst severity recorded will be attributed and used in the by-severity summaries. Similarly, the worst causality (most related to treatment) will be attributed and used in the by-causality summaries. If severity or causality is missing, a conservative approach for AE assessment (taking into account the worst case) will be followed.

Key subject information for participants experiencing SAE with outcome death, SAEs, and AEs leading to discontinuation of IP will be presented in a listing. All the AE will be included in the data listings.

Statistical Analysis Plan

For AEs with partial dates/times, worst case is always assumed; if possibly on-treatment, then on-treatment is assumed, on-treatment AEs will be considered to have the longest possible duration and off-treatment AEs will be considered to have the shortest possible duration. In accordance with this principle, any AEs with incomplete start and end dates/times will be treated as follows:

- AEs with unknown start times, but with start date known, will be imputed with a time of 00:00, unless the start date corresponds to any given dosing date. In this case the start time will be imputed with the time of dosing. If this results in a start date/time after end date/time of the AE, then the time will also be imputed with 00:00.
- AEs with completely unknown start dates will be imputed with the date and time of dosing, unless the end date is known and prior to dosing; in that case the start date will be imputed as the date of Screening and a time of 00:00.
- AEs with partially known start dates/times will be treated as follows:
 - If only the day is missing, then the day will be imputed with the first day of the month, unless the month and year in which the AE started is a month and year in which IP was administered, then the day will be imputed with the first day on which IP was administered in that month. If this results in a start date after the end date, then the day will be imputed with the first day of the month.
 - If only the month is missing and the year is a year in which IP was administered, then the month will be imputed with the first month in which IP was administered. If this results in a start date after the end date of the AE, then the month will be imputed with JAN. If the known year part is not a year in which IP was administered, then the month will also be imputed with JAN.
 - If both the day and month is missing and the year is a year in which IP was administered, then the day and month will be imputed with the day and month of dosing. If this results in a start date after end date, then the day and month will be imputed with 01JAN. If the year is not a year in which IP was administered, then the day and month will also be imputed with 01JAN.
 - If only the year is missing, then the year will be imputed with the year of dosing.

